6.7 CYP Genotyping

The number and percent of patients consenting to CYP2D6 genetic testing as well as the number and percent of patients within each genotype category (poor, intermediate, normal, and ultrarapid metabolizer) will be summarized by treatment group and overall, for the PK set. Consent date, blood sample collection data and all reported genotyping data will be listed separately for patients consenting to CYP2D6 genetic testing.

6.8 Medical History

Separate tabulations of prior and ongoing conditions at screening will be presented by treatment group and overall, for the SAS. Prior conditions are those with a stop date prior to screening and conditions are ongoing otherwise. Tabulations will be presented by SOC and PT in descending frequency of incidence in the pooled mesdopetam arm and then alphabetically for ties. All reported medical history will be listed.

6.9 **Prior and Concomitant Medications**

Prior medications are defined as any medications starting and stopping prior to date of first dose of study drug. Concomitant medications are defined as medications taken on or after the date of first dose of study drug.

Prior and concomitant medications will be presented alphabetically by ATC Level 2 classification followed by ATC level 4 classification and Preferred Name for each treatment group in the SAS.

A separate tabulation will also be provided for all medications reported under ATC Level 1 = Nervous System, Level 2 = Anti-Parkinson Drugs. Medications will be presented by ATC Level 3 and Preferred Name by treatment group and overall.

QMD Ref: Worldwide-TMP-ST-005-7.0 Effective: 12Aug2019	Governing QMD: Worldwide-SOP-ST-001
Confidentiality Statement	
This document is the property of Worldwide Clinical Trials Inc. and may not be duplicated, copied, altered or removed from company without prior approval from Worldwide Quality Assurance or in compliance with Worldwide Standard Operating Procedures.	
REF: Worldwide-TMP-OA-001f-1.3	Page $25 \text{ of } 49$

Worldwide Clinical Trials Controlled Quality Management Document		
WORLDWIDE CLINICAL TRIALS	Sponsor:	Integrative Research Laboratories Sweden AB
	Protocol Number:	IRL790C005
STATISTICAL ANALYSIS PLAN. PHASE 2-3-4		

Average levodopa dose will also be obtained from the medication log. The first reported levodopa dose taken on or after first dose of study drug will be summarized per treatment group alongside clinical characteristics.

All reported medications will be listed. Medication logs will also be reviewed by the Sponsor and any non-permitted medications will be identified and listed separately.

6.10 Exposure to Study Drug

Exposure to study drug will be calculated as follows from the date of last dosing minus the first day of dosing + 1. The exposure calculation will not take into account breaks in therapy.

Exposure	Calculation
Exposure to 5 mg during run-in period (all patients)	Dispensing Date (Visit 2, Day 9) – Date of First Dose + 1
Exposure to randomized dose if the patient did not have a dose reduction	Date of Last Dose – Dispensing Date (Visit 2, Day 9) + 1
Exposure to randomized dose if the patient had a dose reduction	First dispensing date where dose is different to randomized dose – Dispensing Date (Visit 2, Day 9) + 1
Exposure to adjusted dose if the patient had a dose reduction	Date of Last Dose – First dispensing date where dose is different to randomized dose + 1
	(programming checks should be made to ensure the adjusted dose was also dispensed at Visit 3, Day 28)

Exposure to each dose level will be calculated as follows:

In the rare case that a kit was dispensed containing the wrong dose then those records will be excluded from calculations.

Extent of exposure (number of days of exposure to study drug) will be presented by each treatment group and combined based on the randomized treatment. A separate tabulation will also be provided to present the exposure during the run-in period and the period after receiving the randomized dose.

All reported data will also be listed.

QMD Ref: Worldwide-TMP-ST-005-7.0 Effective: 12Aug2019	Governing QMD: Worldwide-SOP-ST-001
Confidentiality	y Statement
This document is the property of Worldwide Clinical Trials Inc. and may no prior approval from Worldwide Quality Assurance or in compl	
REF: Worldwide-TMP-QA-001f-1.3	Page 26 of 49

Worldwide Clinical Trials Controlled Quality Management Document		
WORLDWIDE CLINICAL TRIALS	Sponsor:	Integrative Research Laboratories Sweden AB
	Protocol Number:	IRL790C005
STATISTICAL ANALYSIS PLAN. PHASE 2-3-4		

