9.2. Dosage and administration

The IMP (1 capsule b.i.d.) will be swallowed together with 200 mL of water in the morning and in the afternoon approximately 8 hours apart on each administration day, except for Day 56 and Day 84 when the dose will be taken in the morning at the clinic visit after trough PK sampling.

Dose run-in phase and treatment phase

Treatment allocation throughout the run-in and treatment dosing periods will be managed through the Interactive Response System (IRS) system. During the 9-day run-in phase, the IRS system will ensure all patients allocated to active dose regimen will receive 5 mg mesdopetam b.i.d, followed by the randomized dose at Visit 2 (Day 9). Patients allocated to placebo will receive placebo during the first week run-in and then continue placebo during the whole treatment period. Any dose reduction will also be managed through the IRS system to ensure that blinding is maintained.

If a patient experiences **increased parkinsonism** and/or **consistent increase in motor OFFtime**, during the treatment period from Visit 2 up to Visit 3 (i.e. Day $9 - Day 28 \pm 4 days$), the dosing can be reduced by 2.5 mg b.i.d. A dose reduction is allowed at only one occasion. A review of motor function will be performed at Visit 3.

The following tables give additional information on the two dose phases (Table 2) and the dose decrease guidance (Table 3).

Confidential	Version: 5.0	Page 39 of 74
Protocol: IRL790C005	Date: 5 Mar 2021	e

Table 2: Treatment period – dosing phases

Dose phase	Details
Dose run-in phase: Randomization Day 1. First dose taken Day 1 (evening dose) and last dose taken Day 9 (morning dose).	All patients randomized to mesdopetam will receive 5 mg b.i.d. All patients randomized to placebo will receive placebo b.i.d.
Dosing following Visit 2: First dose taken Day 9 (evening dose) and last dose taken Day 84 (morning dose/at the clinic due to PK sampling)	All patients randomized to mesdopetam will receive mesdopetam 2.5 mg, 5 mg or 7.5 mg b.i.d., as randomized. All patients randomized to placebo will continue with placebo b.i.d.

Table 3: Dose decrease guidance

Treatment period	Dose decrease guidance
Applicable for treatment from Visit 2 (Day 9) until Visit 3 (Day 28 ±4 days):	Decision to reduce the dosing is only allowed from Visit 2 (Day 9) until Visit 3 (Day 28 ± 4 days), and dose reduction is only allowed once.

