10.4. Visit 1 (Baseline, Day 1)

Inclusion and Exclusion criteria will be re-assessed. Eligible patients will be randomized to either trial drug (mesdopetam) or placebo.

The following procedures and assessments will be carried out at Visit 1:

- Inclusion/Exclusion criteria
- Concomitant Medications
- Vital Signs (including supine/standing BP)*
- 12-lead ECG (single assessment)*
- Haematology/Serum Chemistry/Coagulation*
- Dipstick Urinalysis*
- Serum Pregnancy test (if applicable)
- MDS-UPDRS (all parts)
- Modified UDysRS (part 1, 3 and 4)
- Three completed 24-hour patient home diaries collected and assessed for eligibility
- Three empty 24-hour patient home diaries handed out
- CGI-S
- C-SSRS
- AEs/SAEs
- Randomization. Managed through IRS system.
- Dispense IMP. First dose of IMP to be taken in the evening at Day 1.

* If 29 days or more between Screening Visit and Visit 1 (Baseline)

Patient Information Card

Confidential	Version: 5.0	Page 45 of 74
Protocol: IRL790C005	Date: 5 Mar 2021	C C

All study patients randomized will be provided with a Patient Information Card to be carried throughout the study. The card will include the following information:

- That the carrier is participating in a clinical study
- Patient study ID
- That the carrier is potentially treated with IMP
- The name and telephone number of the Investigator
- Name and address of the Sponsor

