10.5. Visit 2 (Day 9 + 2 days)

The following procedures and assessments are to be carried out at Visit 2:

- Allocation of randomized dose of mesdopetam/placebo. Managed through IRS system.
- Dispense and collect empty bottle of IMP
- Concomitant Medications
- AEs/SAEs
- IMP compliance

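### SAP 6.10 dates the switch to a reduced dose by the first kit that differs from the randomised dose. In the 7.5 mg arm that is the Day 1 run-in kit, so a reduced patient gets -7 days on 7.5 mg.

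*SAP*

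**What the plan says.** SAP 6.10 sets total exposure as last dosing date minus first dosing date plus one. It then gives a table of dose-level formulas:

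- Run-in: Visit 2 dispensing date minus first dose date, plus one.
- Randomised dose, no reduction: last dose date minus Visit 2 dispensing date, plus one.
- Randomised dose, with a reduction: the "First dispensing date where dose is different to randomized dose" minus the Visit 2 dispensing date, plus one.
- "Exposure to adjusted dose if the patient had a dose reduction": last dose date minus that same first differing date, plus one.

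Two safeguards go with these formulas. The first is "In the rare case that a kit was dispensed containing the wrong dose then those records will be excluded from calculations". The second, attached to the adjusted-dose row, is that "programming checks should be made to ensure the adjusted dose was also dispensed at Visit 3, Day 28".

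On the run-in, Protocol 9.2 (Table 2) states: "All patients randomized to mesdopetam will receive 5 mg b.i.d". That kit is handed out at Visit 1, where Protocol 10.4 lists "Dispense IMP. First dose of IMP to be taken in the evening at Day 1". The randomised strength arrives only at Visit 2, where Protocol 10.5 lists "Allocation of randomized dose of mesdopetam/placebo. Managed through IRS system". Protocol 9.2 (Table 3) allows one step down between Visit 2 and Visit 3: from 7.5 mg to 5 mg, or from 5 mg to 2.5 mg. Patients on 2.5 mg or placebo stay where they are.

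**The concern.** The rule searches all of a patient's dispensing records for the first one that differs from the randomised dose. In the 7.5 mg arm the Day 1 run-in kit meets that test before any 7.5 mg capsule has been dispensed. The changeover date is then Day 1 rather than the date of the reduction, and the time on 7.5 mg comes out negative.

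The figure at stake is how long patients stayed on the top dose before stepping down. Safety and tolerability over 84 days is a stated secondary objective. Reduction is allowed only for increased parkinsonism or more motor OFF-time, and Protocol 4.3 and 6.2 cite these same effects as the reason for exploring lower doses. For reduced 7.5 mg patients, the rule as written makes that duration meaningless.

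**Working it through.** **Inputs.** First dose and run-in dispensing on Day 1 (Protocol 10.4). Visit 2 on Day 9, window up to Day 11 (Protocol 10.5). Reduction between Day 9 and Day 28 ± 4 (Protocol 9.2). Last dose on Day 84, or Day 82 at the early end of the Visit 5 window (Protocol 6.1 and 10.12). Write D for the changeover date used in the reduced-patient rows.

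**Reproducing the plan's own figures.** Total exposure is 84 - 1 + 1 = 84 days, matching the planned treatment duration. The run-in is 9 - 1 + 1 = 9 days, matching the nine-day run-in in Protocol 9.2. An unreduced patient has 84 - 9 + 1 = 76 days on the randomised dose. The + 1 convention therefore behaves as intended in these rows.

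**7.5 mg arm, reduced patient, rule as written.** The kits are 5 mg on Day 1, 7.5 mg on Day 9, then 5 mg at the reduction. The first that differs from 7.5 mg is on Day 1, so D = 1.

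- Randomised dose: 1 - 9 + 1 = -7 days. With Visit 2 on Day 11 it is 1 - 11 + 1 = -9.
- Adjusted dose: 84 - 1 + 1 = 84 days. With last dose on Day 82 it is 82.

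The date of reduction does not enter either result.

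**Same patient, D limited to dispensing after Visit 2.** For a Day 20 reduction: 20 - 9 + 1 = 12 days on 7.5 mg and 84 - 20 + 1 = 65 days on 5 mg. Across the window:

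| Reduced kit dispensed | Days on 7.5 mg, as written | Days on 7.5 mg, limited | Days on reduced dose, as written | Days on reduced dose, limited |
|---|---|---|---|---|
| Day 14 | -7 | 6 | 84 | 71 |
| Day 20 | -7 | 12 | 84 | 65 |
| Day 21 | -7 | 13 | 84 | 64 |
| Day 28 | -7 | 20 | 84 | 57 |
| Day 32 | -7 | 24 | 84 | 53 |

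Each figure is wrong by D - 1 days, with D the true changeover date: 13 days for Day 14 and 31 for Day 32.

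**5 mg arm.** The run-in kit equals the randomised dose, so the first differing kit is the reduced one. A Day 28 reduction gives 28 - 9 + 1 = 20 and 84 - 28 + 1 = 57 days, as intended.

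**Do the safeguards catch it?**

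- The wrong-kit exclusion does not apply, because the run-in kit is a correct kit.
- The Visit 3 check passes. The reduced dose in this arm is 5 mg, the same strength as the run-in kit.
- A sum check sees nothing. As written the segments add to 9 - 7 + 84 = 86; with the limit, 9 + 12 + 65 = 86. The two post-run-in segments alone add to 77 either way (-7 + 84 and 12 + 65).

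**The case against.** The strongest reply is that the intent is plain from the same table. The run-in has its own row, both randomised-dose rows start from Visit 2 dispensing, and the disputed phrase appears only in rows for patients with a reduction, which cannot occur before Visit 2. A negative duration would be conspicuous, and SAP 6.3.3 requires independent double programming. This stands as a reason to expect that a programmer would notice and correct it. It does not make the written rule right. Both programmers work from the same text, and if they diverge the text favours the wrong answer. SAP section 9 lists exposure as redefined relative to the protocol, so SAP 6.10 is the governing definition.

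A reader might infer more than the documents support:

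- *That the + 1 in each row is a double-counting error.* Segments do sum to 85 days (9 + 76) or 86 against a total of 84. But Table 2 places the Day 9 morning dose in the run-in and the evening dose in the randomised phase, so Day 9 is exposure to both. The SAP does not require the segments to sum to the total, which it computes separately. Dropping the + 1 would give a run-in of 9 - 1 = 8 days, against the protocol's nine.
- *That placebo patients are credited with 5 mg.* The run-in row's title covers all patients, but displays are by treatment group with placebo in its own column (SAP 6.3.6). This is a label.
- *That the rule fails everywhere except the 5 mg arm.* A 2.5 mg patient's dose is kept on a reduction request, so there is no true reduction to date. Day 1 would be picked up only if such a patient were flagged as reduced, and the documents do not settle that.
- *That the 7.5 mg arm's overall exposure is pulled down.* Total exposure uses only first and last dosing dates.

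**Conclusion.** The point holds as a narrow error in a stated rule. Read literally, SAP 6.10 gives a reduced 7.5 mg patient -7 days on 7.5 mg and 84 days on the adjusted dose, where a Day 20 reduction should give 12 and 65. This assumes Visit 2 on Day 9, last dose on Day 84, and the run-in kit held as an ordinary dispensing record.

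The effect is descriptive and limited to dose-level exposure in reduced 7.5 mg patients. Their number is not given, so no effect on an arm summary can be stated. SAP 6.10 also does not spell out how the dose-level figures will be displayed. It names a tabulation of the run-in and the period after the randomised dose is received. If that period is shown only as one combined figure, the error cancels; if the two doses are shown separately, it appears. The adjusted dose groups (SAP 6.2.16) rest on the reduction recorded at Visit 3, so they, the safety summaries by adjusted dose and the efficacy analyses do not depend on this date.

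**What to change.** In both reduced-patient rows of SAP 6.10, replace the phrase with: *first dispensing date after the Visit 2 dispensing on which the dispensed dose is lower than the randomised dose*. The timing limit removes the run-in kit from the search, and requiring a lower dose ties the date to an actual step down.

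Keep the + 1 convention. Relabelling the run-in row as 5 mg or placebo is optional and clerical.

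The cost is one qualifier in two rows and the matching line of derivation code. No new data are needed and no other analysis changes.

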6.11 Treatment Compliance

Treatment compliance will be calculated as follows:

• Compliance (%) = (Actual number of doses taken / Expected number of doses) *100

The actual number of doses = Sum of quantity dosed across all records.

The expected number of doses is obtained as follows:

- If the last dose is a morning dose: [(End of treatment (Visit 5) date Date of first dose 1) * 2] + 2
- If the last dose is an evening dose: [(End of treatment (Visit 5) date Date of first dose 1) * 2] + 3

The expected number of doses is obtained by first calculating the number of full days on study treatment and multiplying by 2 doses per full day per protocol. Then one dose is added for the Day 1 evening dose and either one dose is added if the last dose was a morning dose, or two doses are added if the last dose was an evening dose.

Compliance (%) will be summarized by treatment group, combined treatment groups, and overall based on the actual treatment received for the SAS and will be presented following the decimal convention in Section 6.3.5. The number and percent of patients with compliance <80% will also be provided by treatment group, combined treatment groups, and overall.

All drug accountability data will be listed as recorded on the eCRF.

6.12 Primary Efficacy Analyses

All applicable statistical tests will be performed at a local significance level consistent with an overall FWER of 5% and the multiple testing strategy described in Section 0. All comparisons between treatments will be reported with 95% confidence intervals (CI) for the difference. All efficacy analyses will be performed by randomized treatment group and adjusted dose group for patients in the FAS, as well as all active doses grouped compared to placebo.

6.12.1 Estimand

The main study estimand will follow the 'treatment policy' strategy to estimate the treatment effect of mesdopetam (2.5 mg, 5 mg, or 7.5 mg b.i.d.) compared to placebo b.i.d. (treatment) on the

QMD Ref: Worldwide-TMP-ST-005-7.0 Effective: 12Aug2019	Governing QMD: Worldwide-SOP-ST-001
Confidentiality	/ Statement
This document is the property of Worldwide Clinical Trials Inc. and may n prior approval from Worldwide Quality Assurance or in compl	1 1 1
REF: Worldwide-TMP-QA-001f-1.3	Page 27 of 49

Worldwide Clinical Trials Controlled Quality Management Document		
WORLDWIDE CLINICAL TRIALS	Sponsor:	Integrative Research Laboratories Sweden AB
	Protocol Number:	IRL790C005
STATISTICAL ANALYSIS PLAN. PHASE 2-3-4		

change from baseline to Week 12 (population-level summary) in average daily ON-time (hours) (variable) in patients with Parkinson's Disease exhibiting ON-phase dyskinesia, as defined by the inclusion/exclusion criteria (population) regardless of missing motor diary data, any permitted dose reduction, use of amantadine (if any), or discontinuation for any reason.

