10.13. Visit 6 (Follow Up 5-8 days after End-of-Treatment)

The following procedures and assessments are to be carried out at Follow Up:

- Concomitant Medication
- Weight
- Vital Signs (including supine/standing BP)
- Physical Examination
- 12-lead ECG
- Haematology/Serum Chemistry (including prolactin)/Coagulation
- Dipstick Urinalysis
- AEs/SAEs

NOTE: Patients that discontinue IMP early for any reason should if possible, undergo Visit 6 assessments 5-8 days after the last dose of IMP.

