10.14. Early Termination Visits

Patients have the right to withdraw from the trial at any time and for any reason. If a patient discontinues the IMP early, a safety follow-up visit (according to follow-up, Visit 6) should if possible be scheduled within 5-8 days after the last intake of the IMP.

Confidential	Version: 5.0	Page 48 of 74
Protocol: IRL790C005	Date: 5 Mar 2021	5

11.STUDY PROCEDURES / EVALUATIONS

Signed informed consent must be obtained before any screening procedures are initiated. The informed consent procedure is further described in Section 17.

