14.3.2. Full analysis set

The Full Analysis Set (FAS) will include all randomized patients who received at least 1 dose of IMP and who provided at least one post baseline assessment. All efficacy analyses will be presented by allocated treatment for patients in the FAS population.

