6.1.2 Full Analysis Set

The Full Analysis Set (FAS) will include all randomized patients who received at least 1 dose of IMP and who provided at least one valid post baseline diary. All efficacy analyses will be presented by randomized treatment for patients in the FAS.

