6.2.3 Early Withdrawal Assessments

Early withdrawal assessments will be summarized as a separate visit and will be mapped to an expected visit window as follows:

- During the run-in period
- Post run-in and prior to visit 3
- At visit 3 or post visit 3

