6.12.3 Primary Analysis

The number and percent of patients with valid diaries will be tabulated by treatment group and visit and a listing of diary completion will be provided. Descriptive statistics for the actual values by visit (including baseline) and change from baseline to each post-baseline visit (Visits 3, 4 and 5/EOT) in average daily ON-time without troublesome dyskinesia (hours) will be presented.

Change from baseline in average daily ON-time without troublesome dyskinesia (hours) will be analysed using a mixed model for repeated measures (MMRM) for all patients in the FAS. Change from baseline to Week 12 is the timepoint of interest for this analysis. Any missing data is assumed to be missing at random (MAR) for this analysis.

The model will include randomized treatment (2.5 mg, 5.0 mg, 7.5 mg, or placebo b.i.d.), visit, country, and treatment by visit interaction as explanatory, fixed effect variables. Country will be

Worldwide Clinical Trials Controlled Quality Management Document		
WORLDWIDE CLINICAL TRIALS	Sponsor:	Integrative Research Laboratories Sweden AB
	Protocol Number:	IRL790C005
STATISTICAL ANALYSIS PLAN. PHASE 2-3-4		

weighted by the number of patients participating from each county. Baseline value for average daily hours of ON time without troublesome dyskinesia will be included as a continuous covariate along with the randomisation stratification factor of daily hours spent in ON-time with troublesome dyskinesia (<6 hours, \geq 6 hours).

An unstructured covariance matrix will be assumed for within-patient correlation over time. If the model fails to converge, the first approach for which the model converges among the following will be used: banded Toeplitz (TOEP), compound symmetry (CS) and variance component (VC).

The LS mean estimate, corresponding SE, and 95% CI for the change from baseline at each postbaseline visit will be obtained from the model and presented for each treatment group. The estimated treatment difference for each dose level compared to placebo and the combined dose levels compared to placebo, the corresponding SE, and p-value will also be presented by visit.

A line plot showing the LS mean ($\pm 95\%$ CI) change from baseline at each visit for each treatment group will also be provided.

The following is the sample SAS code that will be used for this analysis:

```
PROC MIXED DATA= analysis (where = (avisitn ne 0));
    ODS OUTPUT LSMeans=LSMeans Diffs=Diffs LSMEstimates=Estimates;

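### The main estimand is labelled treatment policy for discontinuation, but no diaries are planned after stopping, the MMRM assumes MAR, and the FAS rule keeps the earliest dropouts out of both imputation analyses

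*SAP*

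**What the plan says.** **Estimand and estimator.** SAP 6.12.1 sets a treatment-policy strategy for the change to Week 12 in diary ON-time, "regardless of missing motor diary data, any permitted dose reduction, use of amantadine (if any), or discontinuation for any reason". SAP 6.12.3 estimates it with an MMRM on the post-baseline visits: "Any missing data is assumed to be missing at random (MAR) for this analysis".

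**Data after stopping.** Footnote 12 of the protocol's schedule of procedures places diaries before Visits 1, 3, 4 and 5 only, 12 in all. Protocol 10.14 says: "If a patient discontinues the IMP early, a safety follow-up visit (according to follow-up, Visit 6) should if possible be scheduled". Protocol 10.13 says: "Patients that discontinue IMP early for any reason should if possible, undergo Visit 6 assessments 5-8 days after the last dose of IMP". The Visit 6 list covers concomitant medication, weight, vital signs, examination, ECG, laboratory tests, urinalysis and adverse events. It has no diary. Protocol 7.4 also has the investigator complete the study-termination part of the CRF after early IMP discontinuation.

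**Population.** SAP 6.12 says: "All efficacy analyses will be performed by randomized treatment group and adjusted dose group for patients in the FAS". SAP 6.1.2 limits the FAS to randomised patients who "received at least 1 dose of IMP and who provided at least one valid post baseline diary". Protocol 14.3.2 has patients who "received at least 1 dose of IMP and who provided at least one post baseline assessment". This difference is not among the 14 changes listed in SAP Section 9.

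**Sensitivity analyses.** SAP 6.12.4.1 plans control-based imputation and describes its result as conservative. SAP 6.12.4.2 plans a tipping-point analysis, run only if the primary analysis significantly favours mesdopetam. Neither names a population wider than the FAS. SAP 6.2.3 provides windows for withdrawal during run-in and "Post run-in and prior to visit 3".

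**The concern.** A treatment-policy strategy for discontinuation needs outcomes observed after discontinuation. None is scheduled. A MAR model then fills the gap from similar patients still under observation, who are mostly still on treatment, which comes close to a hypothetical strategy. Missing diary data is also listed as though it were an intercurrent event, when it is a missing-data problem.

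The sensitivity analyses are meant to test the MAR assumption. Because they run on the FAS, a patient who leaves before the first post-baseline diaries (the week before Visit 3) is neither imputed from placebo nor shifted by δ. The test is therefore weakest where dropout is earliest. The headline effect could be reported under an estimand that the data do not identify, supported by a stress test milder than its description.

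**Working it through.** **Inputs from the documents** (Protocol 14.2, SAP 4): effect E = 3 h, SD 3.5, 35 per group, 31 evaluable, 10% expected dropout. SAP 4 reports dropout above expectation and an increase to 154 patients, but gives no rate or timing.

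**Assumed:** d = active-arm dropout; r = share of benefit kept after stopping; f = share of dropouts leaving before the Visit 3 diaries; ρ = correlation between visits given baseline (exchangeable, 0.5–0.7). Dropouts who are not early have Visit 3 data only.

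**1. The plan's own figure.** SE = 3.5 × √(2/31) = 0.889 h. Then 3/0.889 − 1.96 = 1.41, which gives 92.1% power. The stated 92% reproduces. It is power for completers at the full 3 h, with no dilution for discontinuation.

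**2. MAR estimate minus treatment-policy effect, dropout unrelated to outcome.** MAR returns about E; the treatment-policy effect is E(1 − d) + d·r·E. Gap = d·E·(1 − r).

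| d | r = 0 | r = 0.5 | r = 1 |
|---|---|---|---|
| 10% | 0.30 h | 0.15 h | 0 |
| 20% (assumed) | 0.60 h | 0.30 h | 0 |

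**3. Dropout related to outcome.** Let dropouts have effect g at Visit 3 and none later. MMRM ≈ 3 − ρ·d·(3 − g); treatment policy = 3(1 − d); gap = d·[3 − ρ(3 − g)].
- With g = 0 and d = 0.10, the gap is 0.15, 0.12 and 0.09 h at ρ = 0.5, 0.6 and 0.7.
- The gap is zero at g = 3 − 3/ρ = −3.0, −2.0 and −1.3 h respectively, and changes sign below that.

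**4. Control-based estimate on the FAS and on all dosed patients.** The SAP 6.12.4.1 regression is fitted on placebo and conditions on earlier diary hours. An active patient with benefit E at Visit 3 is therefore imputed with about ρE at Week 12, so 50–70% of the benefit is carried forward. A patient with no post-baseline diary would be imputed at the placebo mean.
- All dosed = (1 − d)E + d(1 − f)ρE
- FAS = the same quantity divided by (1 − d·f)

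At d = 0.10 and ρ = 0.6:

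| f | All dosed | FAS |
|---|---|---|
| 0 | 2.70 + 0.18 = 2.88 h | 2.88 h |
| 0.5 | 2.70 + 0.09 = 2.79 h | 2.79/0.95 = 2.94 h |
| 1 | 2.70 h | 2.70/0.90 = 3.00 h |

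Over ρ = 0.5–0.7 the f = 0.5 row is 2.78–2.81 h against 2.92–2.95 h. At an assumed d = 0.20, f = 0.5 and ρ = 0.6, all dosed is 2.40 + 0.18 = 2.58 h and the FAS gives 2.58/0.90 = 2.87 h. A large-sample simulation of the sequential placebo regression (SD 3.5, 400,000 per arm) agreed with the d = 0.10 formulas within 0.01 h.

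At f = 1 the FAS analysis returns the MAR answer exactly. The sample imputation code could handle a patient with baseline data only; it is the FAS rule that removes such patients.

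**The case against.** The strongest reply is that an estimand names a target, and missing values after discontinuation are an estimation problem for which the SAP plans two MNAR analyses. On that view the weak part is the primary estimator, and collecting diaries after stopping would be an alternative remedy. Nothing in the documents forbids such diaries, and SAP 6.17.1 tabulates withdrawal of study drug separately from withdrawal from the study. That is fair as far as it goes. But no such diaries are scheduled, and the control-based model is a sensitivity analysis that leaves out the earliest dropouts.

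Four narrower points have some force:
- The protocol's FAS wording is ambiguous. If a post-baseline assessment means an efficacy assessment, that FAS would already exclude most early leavers, since the first efficacy measures belong to Visit 3. The SAP's FAS still excludes them. Its narrower wording could also drop patients with Visit 3 ratings but no valid diary from the secondary analyses.
- SAP 6.2.3 is a mapping rule. It provides for early withdrawals but does not predict how many.
- The sizes are modest: 0.15–0.30 h is 0.17–0.34 of the 0.89 h standard error, and Protocol 11.2.3.1 treats 1 h as clinically meaningful. The f = 1 case is an extreme.
- The primary model, its dataset and its p-value would not change. A patient without a post-baseline diary contributes no change-from-baseline record in any case.

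These limit the size of the problem. They do not remove the mismatch.

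**Conclusion.** The point holds and should be fixed. The treatment-policy label suits permitted dose reduction and amantadine use, because diary data collected after those events stay in the primary analysis. It does not suit discontinuation: the planned data do not identify that effect, and the MAR MMRM estimates something close to a hypothetical one. At 3 h and 10% dropout unrelated to outcome, the difference is 0 to 0.30 h, depending on how much benefit persists. If outcome drives dropout it can shrink or change sign, so it cannot be assumed harmless or one-sided.

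For patients who leave before the Visit 3 diaries, the control-based analysis is not the conservative check it is described as. Restricting it to the FAS raises the estimate by 0 to 0.30 h at 10% dropout. The mismatch follows directly from the documents; its size rests on assumed dropout timing, persistence of benefit and visit correlation.

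**What to change.** - In SAP 6.12.1, keep treatment policy for permitted dose reduction and amantadine use. State a hypothetical strategy for IMP discontinuation, as estimated by the MAR MMRM. Make clear that a patient who leaves after a dose reduction or amantadine use then counts as a discontinuation.
- Remove missing diary data from the list of intercurrent events.
- Run the control-based and tipping-point analyses on all randomised and dosed patients. Baseline diaries exist for them, since Protocol 11.2.3.1 requires two valid ones for inclusion.
- Present the control-based result as an assumption-based approximation to the treatment-policy effect, and note that its regression carries forward about 50–70% of an active dropout's earlier benefit (visit correlation 0.5–0.7).
- List the FAS change in SAP Section 9.

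The cost is SAP wording, a wider input population for two planned analyses and one line in Section 9. No new data are needed, which is the reason to prefer this to adding diaries after discontinuation. The downside is a control-based estimate that would probably be slightly smaller, by 0 to 0.30 h at 10% dropout.
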